4.9. BRIEF PAIN INVENTORY (BPI) SHORT FORM

The BPI Short Form rapidly assesses the severity of pain and its impact on functioning. The BPI questionnaire will be used at Baseline, Week 4, Week 12, Week 18 and Week 24 visits. If applicable, the test will also be performed at the Early Termination visit.

Four severity items will be investigated by the responses to the worst, least and average pain in last 24 hours and the pain right now (Questions 3, 4, 5 and 6). The higher score indicates worse pain. A pain severity score will be calculated as the mean of the non-missing 4 severity items.

In addition, the average pain interference score will be derived as the average of the responses to the 7 components to Question 9 (Cleeland 2009). If there are 3 or fewer responses, then the pain interference score will not be calculated. The higher score indicates more pain interferes with daily functioning.

For each visit changes from baseline will be calculated for the pain severity and pain interference scores. Both the pain severity score and the pain interference score are exploratory endpoints.

4.10. WORK PRODUCTIVITY AND ACTIVITY IMPAIRMENT QUESTIONNAIRE: SPECIFIC HEALTH PROBLEMS (WPAI: SHP)

The WPAI questionnaire is a validated instrument to measure impairments in work and activities. The questionnaire will be used at Baseline, Week 4, Week 12, Week 18 and Week 24 visits. If applicable, the test will also be performed at the Early Termination visit.

Outcomes are expressed as impairment percentages, with higher numbers indicating greater impairment and less productivity, i.e., worse outcomes. There are 6 questions defined as:

Questions	Definition
1	currently employed (Yes/No)
2	hours missed because of problems associated with your PMM
3	hours missed because of other reasons
4	hours actually worked
5	how much did your PMM affect productivity while working (scale of 0 [no effect on my work] to 10 [completely prevented me from working])

Questions	Definition
6	how much did your PMM affect regular activities (scale of 0 [no effect on my daily activities] to 10 [completely prevented me from doing my daily activities])

The following 4 scores are exploratory endpoints and are calculated from the responses, the first 3 will only be calculated if the subject is employed:

Score	Equation
Percent work time missed due to PMM	$100 \times \frac{Q2}{(Q2 + Q4)}$
Percent impairment while working due to PMM	$100 \times \frac{Q5}{10}$
Percent overall work impairment due to PMM	$100 \times \left(\frac{Q2}{(Q2 + Q4)} + \left[\left(1 - \left(\frac{Q2}{(Q2 + Q4)} \right) \right) \times \left(\frac{Q5}{10} \right) \right] \right)$
Percent activity impairment due to PMM	$100 \times \frac{Q6}{10}$

Generally, if a response to a question used in the calculation of a score is missing, the score will be set to missing. The exception to this is the calculation of the percent overall work impairment due to PMM score; if all working hours are missed due to problems associated with PMM (i.e., Question 2≠0 and Q4=0) then $(1 - (Q2 / (Q2 + Q4))) = 0$, and so it does not matter if Question 5 (how much did your PMM affect productivity while working) is missing or has a value. Indeed, it is anticipated that the Question 5 response will be missing if they had not worked. In such situations the percent overall work impairment due to PMM will be entirely based on work time missed due to PMM i.e., 100%.

For each visit changes from baseline for each score will be calculated.

4.11. PMM PHENOTYPIC DESCRIPTION

The phenotypic state of the subject’s disease is rated using 3 questions taken from the Newcastle Mitochondrial Disease Adult Scale. The questions will be completed at Baseline and Week 24 visits. If applicable, the test will also be performed at the Early Termination visit. Where possible the same physician should ask the questions on both occasions to ensure consistency of interpretation.

The 3 questions relate to exercise tolerance, gait stability and myopathy and asked in relation to the previous 4-weeks. Each question has 6 levels (0 to 5) and higher scores indicate a worse rating.

Changes from baseline to Week 24 will be calculated for the 3 phenotypic questions.

5. PHARMACOKINETIC ASSESSMENT

Plasma mavodelpar concentrations will be determined from samples taken during the study. Samples may be analysed for metabolites, but any analysis of metabolite concentrations will not be part of the CSR and are not detailed in this SAP.

Pre-dose and post-dose blood samples at 1, 2, 3 and optional 4 hours will be taken on Day 1 and at the Week 12 and Week 24 visits. On the other visits, a single sample can be taken at any time post-dose. Sample collection times will be recorded.

The data will be used for a population pharmacokinetic (PK) analysis which will be detailed in a separate population PK analysis plan and reported separately.

6. SAFETY ASSESSMENTS

6.1. ADVERSE EVENT

The incidence, causality and severity of treatment-emergent adverse events (TEAEs), including treatment-emergent serious adverse events (TESAEs) and adverse events of special interest (AESI), will be investigated.

AESI are those of scientific and medical concern specific to mavodelpar and include:

- Changes in laboratory parameters of muscle injury associated with clinically significant adverse events (AEs)
- Changes observed after baseline in formation or exacerbation of cataracts or, visual acuity. A spherical equivalent change of ≥ 0.75 diopters will be considered to be a clinically significant change regardless of changes in lens clarity.
- Occurrence of fractures after baseline

AESI will be identified on the eCRF and will be reported in the same way as serious adverse events (SAEs).

6.2. LABORATORY EVALUATIONS

Laboratory evaluations are done throughout the study (as detailed in the schedule of assessments) and include:

- Hematology parameters
- Biochemistry parameters, including
 - the osteoblastic bone marker - bone specific alkaline phosphatase (BSAP)
 - calcium markers - parathyroid hormone and vitamin D
- Urinalysis parameters, including:
 - the osteoclastic bone marker - Urine N-terminal telopeptide (NTx), via a morning second void

Changes from baseline will be calculated for each laboratory parameter for each scheduled visit. The last on-treatment measurement will also be identified.

Laboratory values that are less than the lower limit of quantification (LLOQ) will be set to the LLOQ for the calculation of descriptive statistics. The original value will be displayed in listings.

6.3. DUAL-ENERGY X-RAY ABSORPTIOMETRY (DXA) SCAN

DXA scans will be performed on a subset of subjects at Screening and at Week 24, or the Early Termination visit provided the subject has received at least 20 weeks of study drug.

Baseline will be the measurement collected at Screening. The BMD, T-score and Z-score will be measured for 5 spine regions (L1-L4 and total) and for 2 hip regions (total and femoral neck).

Changes from baseline and percent changes from baseline to end of treatment will be calculated for each parameter.

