14. Clinically significant cardiac disease and/or clinically significant ECG abnormalities including a screening QTcF of ≥ 450 msec, 2nd degree heart block, symptomatic tachyarrhythmia or unstable arrhythmia that in the opinion of the Investigator should exclude the subject from completing the study exercise tests (i.e., 12MWT and 30STS tests). *(Subjects with right bundle branch block, left fascicular block and long PR interval which are common in PMM may be enrolled if the Investigator considers that the condition would not compromise safety or interfere with the tests and interpretations of this study.)*
15. Any condition possibly reducing drug absorption (e.g., gastrectomy or increased motility).
16. Evidence of hospitalization for rhabdomyolysis within the year prior to enrolment.
17. Positive HBsAg and HBcAb at Screening, or positive for hepatitis C or HIV at Screening.
18. Pregnant or nursing females.
19. History of sensitivity to PPAR agonists.

20. Donation or intent to donate blood, or blood components during the study or within one month after completion of the study.
21. A history of drug dependency. Use of opiates/cannabis for medical reasons is acceptable with prescription evidence or at the Investigators discretion.
22. A history of alcohol dependency.
23. Significant impairment due to central or peripheral nervous system involvement that would interfere with the exercise tests.
24. Significant weakness not caused by the underlying primary muscle disease such as post stroke or neurogenic weakness.
25. Have had an organ transplant.
26. Are not eligible or have a contraindication for cataract surgery.
27. A history of osteoporosis as evidenced by non-traumatic (stress) fractures or a prior T-score of -2.5 or worse which has not been adequately addressed.
28. Inability to comprehend or unwilling to follow the study requirements including restrictions on treatments, attendance at the study center, completion of questionnaires and participation in laboratory testing as called for by the protocol.
29. Any other severe acute or chronic medical or psychiatric condition or laboratory abnormality that may increase the risk associated with study participation or investigational product administration or may interfere with the interpretation of study results and, in the judgment of the Investigator, and in discussion with the Medical Monitor, would make the subject inappropriate for entry into this study.

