3.2.6. REN001-201-DXA Sub-Study Endpoints

Change from baseline to end of treatment in BMD, as measured by DXA, in the following:

- Lumbar spine (L1 to L4) BMD
- Total hip BMD and the femoral neck BMD (in the non-dominant hip)
- Total hip, lumbar spine, and femoral neck T-scores and Z-scores.

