8.2. GENERAL METHODS

All statistical testing will be at the 5% level of significance (2-sided) and all point estimates for the comparison between treatment groups will be accompanied by 2-sided 95% confidence intervals. To preserve the Type 1 error a fixed sequence testing procedure will be adopted. Testing will be on the FAS. The order of testing for the primary and secondary endpoints will be:

1. Change from Baseline at Week 24 in distance walked during the 12MWT
2. Change from Baseline at Week 24 in the PROMIS T-score

Continuous variables will be summarized using the number of non-missing observations (n), mean, SD, median, minimum, and maximum. Categorical variables will be summarized using counts and percentages.

Unless otherwise specified, the estimated mean and median for a set of values should be displayed to 1 more decimal place than the original values, and SD should be displayed to 2 more decimal places than the original values. The minimum and maximum should be displayed to the same number of decimal places as the original values. Deviations from this convention may arise to take account of the relevance of the precision (e.g., the distance walked in the 12MWT is reported to the nearest cm, but there is no relevance in presenting the mean to the nearest mm). These deviations from convention will be documented in the relevant analysis sections below.

Percentages will be displayed with 1 decimal place; except percentages will not be presented when the count is zero and 100% will be presented as an integer. Unless stated otherwise, percentages of subjects will be based on the number of subjects with non-missing data in the analysis set used for the presentation.

Baseline will be taken as the last available non-missing assessment prior to study drug administration (Day 1). Although the time of completion is not collected for QoL questionnaires (MFIS, PGIS, PROMIS, SF-36, BPI or WPAI:SHP), any completed on Day 1 will be deemed suitable for baseline as the questionnaires are requested in the protocol to

be completed prior to dosing and, even if after dosing, there is no anticipated effect after a single dose.

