Unless stated otherwise, an on-treatment measurement will be any measurement collected (including scheduled and unscheduled visits) up to the date of last dose plus one day for safety endpoints and plus seven days for efficacy endpoints. Drug interruptions will not be considered, i.e., data will not be excluded during a drug interruption if the subject resumes study treatment.

In by-visit summary tables, the baseline will be summarized using all available data, but also for each visit using only the baseline data from subjects with available data at the visit; hence the mean change from baseline will equal the mean observed visit value – mean baseline value.

Throughout this document ‘change from baseline’ refers to the actual change from baseline (i.e., observed visit value – baseline value).

Summary tables will be split by treatment group (REN001 100 mg and placebo). Baseline summary tables (disposition, demography, baseline characteristics, medical history and prior medications) will also include an overall summary.

All data for randomized subjects, who receive at least one dose of study medication, will be listed. For screen failure subjects only disposition (including reason for screen failure), demographics and protocol deviations will be listed.

Data listings will be ordered by treatment group and subject. A subject’s mutational genotype (m.3243A>G, m.8344A>G, mt deletion or Other) will be identified on the listings. Data listings will present study days in addition to dates, where study day is derived as per SDTM guidelines i.e., study day is derived as (assessment date – first day of dosing +1) after the start of dosing and as (assessment date – first day of dosing) before the start of dosing. Hence, the first day of dosing will be identified as Study Day 1.

All statistical analyses will be performed using SAS® (Version 9.4 or higher, SAS Institute Inc., Cary, NC, USA).

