12.3. DUAL ENERGY X-RAY ABSORPTIOMETRY (DXA) SCAN

Observed, change from baseline values and percent changes from baseline values for the DXA endpoints will be summarized for the DXA ScAS. The summary will be presented overall within the treatment group and by sex and menopausal status (i.e., men, pre-menopausal women and post-menopausal women).

A box and whisker plot will be presented for each of the parameters measuring the total spine and the 2 hip regions (total and femoral neck), for the DXA CScAS. The whiskers will display the 5th and 95th percentiles and outliers will be identified on the plot with subject ID. The plot will present the 2 visits alongside one another for each treatment group. The plot will be repeated by sex and menopausal status.

For the DXA CScAS, the study day of the follow-up DXA scan will be summarized using descriptive statistics. In addition, the number and percentage of subjects will be presented for the following relating to when they have their scan:

- whilst on treatment in REN001-201 (within 7 days of their last dose) and have not yet transitioned to the mavodelpar open-label study
- after discontinuing treatment in REN001-201, but having transitioned to the mavodelpar open-label study
- after discontinuing treatment in REN001-201 (> 7 days after their last dose) and not transitioned to the mavodelpar open-label study

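### Percent change from baseline is planned for DXA T-scores and Z-scores, which can be negative or zero, so bone loss can be tabulated as a gain

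*SAP*

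**What the plan says.** SAP section 6.3 lists the DXA measures: "The BMD, T-score and Z-score will be measured for 5 spine regions" and for two hip regions. Its next paragraph gives the derivation rule: "Changes from baseline and percent changes from baseline to end of treatment will be calculated for each parameter".

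Section 3.2.6 defines the sub-study endpoints as changes from baseline to end of treatment. Besides BMD at the spine and hip it includes "Total hip, lumbar spine, and femoral neck T-scores and Z-scores".

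Section 12.3 sets the reporting: "Observed, change from baseline values and percent changes from baseline values for the DXA endpoints will be summarized for the DXA ScAS". The summary is given by treatment group, overall and by sex and menopausal status.

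Section 8.2 supplies the statistics: "Continuous variables will be summarized using the number of non-missing observations (n), mean, SD, median, minimum, and maximum". It also says that the phrase 'change from baseline' "refers to the actual change from baseline", that is, observed minus baseline. The SAP gives no formula for percent change and no rule for a baseline of zero.

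**The concern.** Percent change needs a ratio scale with a positive baseline. BMD meets that condition. T- and Z-scores are standardised distances from a reference mean, so zero is an ordinary value and negative values are common. Dividing by a negative baseline reverses the sign, dividing by a value near zero inflates the result without limit, and dividing by zero gives nothing. When subjects with positive and negative baselines are averaged, equal losses cancel.

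Negative scores will be present. Exclusion criterion 27 in Protocol section 4.2 removes subjects with a history of osteoporosis shown by non-traumatic fractures or by "a prior T-score of -2.5 or worse which has not been adequately addressed". Subjects with scores between -2.5 and 0 can therefore enter, as can those at or below -2.5 whose condition has been addressed.

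Protocol section 1.4 says it is not known whether the drug affects bone mineral density, and the sub-study is meant to inform that question. A table row that can show a loss as a gain, or show a between-arm difference produced only by baseline scores near zero, does not serve that purpose.

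**Working it through.** The plan states no figure on this point to reproduce, and the sub-study has no sample-size calculation (SAP section 3.5). The check has three steps.

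**1. Single-subject arithmetic (no distributional assumption).** Percent change = 100 × (follow-up − baseline) / baseline, for a loss of 0.2 score units. The SAP does not state the denominator; the usual signed baseline is taken first, and the absolute value of the baseline is shown as the alternative.

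| Baseline | Follow-up | Signed denominator | Absolute-value denominator |
|---|---|---|---|
| -2.0 | -2.2 | +10% | -10% |
| -1.0 | -1.2 | +20% | -20% |
| -0.5 | -0.7 | +40% | -40% |
| -0.1 | -0.3 | +200% | -200% |
| 0.0 | -0.2 | undefined | undefined |
| +0.1 | -0.1 | -200% | -200% |
| +0.5 | +0.3 | -40% | -40% |
| +1.0 | +0.8 | -20% | -20% |

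Two subjects who each lose 0.2 units, one from -1.0 and one from +1.0, average (+20% − 20%) / 2 = 0%. Their mean absolute change is -0.2.

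**2. The same loss expressed in BMD.** Assume a reference mean of 1.0 g/cm² and SD of 0.11 g/cm² (not in the documents). A loss of 0.2 T-score units is then 0.2 × 0.11 = 0.022 g/cm². At T = -1 the BMD goes from 0.890 to 0.868, which is -2.47%. At T = +1 it goes from 1.110 to 1.088, which is -1.98%. At T = -2 it is -2.82%. Percent change in BMD keeps the sign of a loss and stays in a narrow range.

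**3. What the arm means would look like.** The documents give no baseline distribution for the scores, so all inputs here are assumptions: 40 subjects per arm, baseline SD 1.0, change SD 0.15, scores recorded to one decimal, zero baselines dropped, 4,000 simulated arms per row, signed denominator.

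| Baseline mean | True mean change | Wrong sign, among non-zero changes | Arms with positive mean percent change | Spread of arm means |
|---|---|---|---|---|
| 0 | -0.1 | 50% | about 50% | -21% to +21% (95% range) |
| -0.5 | -0.1 | 70% | about 69% | |
| -1.0 | -0.1 | 85% | about 83% | median +7% |
| 0 | -0.2 | | 51% | -23% to +24% (5th to 95th percentile) |
| -0.5 | -0.2 | | 76% | -14% to +32% (5th to 95th percentile) |
| -1.0 | -0.2 | | 91% | -3% to +32% (5th to 95th percentile) |
| -1.5 | -0.2 | | 97% | +2% to +29% (5th to 95th percentile) |

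Between 1% and 4% of baseline scores round to 0.0 and have no percent change. In the runs with a true mean change of -0.1 at the baseline means shown, the mean absolute change was negative in every simulated arm.

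The absolute-value denominator corrects the sign but not the instability. At a baseline mean of 0 and a true mean change of -0.2, arm means still ran from -71% to -31% (5th to 95th percentile) for the same underlying loss.

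**The case against.** The strongest reply is that nothing depends on these rows. The sub-study is exploratory and its size has no statistical basis. SAP section 12.3 sets no test, model or threshold for DXA, and the fixed testing sequence covers only 12MWD and the PROMIS T-score. The same summary also gives observed values, absolute change and valid percent change in BMD, so a reader who uses those rows will see the loss. This stands, and it limits how much the error matters.

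The sign reversal also rests on the signed denominator, which the SAP does not state. That is a fair qualification: with the absolute-value denominator, positive arm means almost disappear (under 0.5% of arms, with a true mean change of -0.1). But the unstable means and the undefined zero baselines remain.

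The simulated percentages are illustrations, not estimates for this trial. Medians are also required and behave differently: at a baseline mean of 0 and a true mean change of -0.1, the arm median was positive in only 11% of arms. They give no protection at lower baselines, however: with a baseline mean of -1.0 and a true mean change of -0.2, nearly all arm medians were positive.

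Finally, the table shells and the separate DXA sub-study protocol are not among the documents reviewed and could narrow the output. The SAP text should still be right by itself. It already treats another standardised score correctly: section 4.2 derives only absolute change for the PROMIS T-score, whereas section 4.1 derives both absolute and percent change for walk distance.

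**Conclusion.** The concern holds. Followed as written, SAP sections 6.3, 3.2.6 and 12.3 together produce percent-change summaries for T- and Z-scores that cannot be interpreted. That conclusion needs no assumption about the data beyond some scores being negative or near zero, which the eligibility criteria allow. The reversed sign additionally assumes the usual signed denominator; instability and undefined values arise with either denominator. How often an arm mean would mislead depends on the unknown baseline distribution: from about half of arms at a baseline mean of 0 to 83% to 91% at -1.0, on the assumed inputs.

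The fault is confined to the percent-change rows for the two scores. BMD results, absolute changes in the scores, and the primary and secondary analyses are unaffected. It should be corrected because it is part of the bone-safety output, but it does not threaten the trial's main conclusions.

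**What to change.** In SAP section 6.3, state that percent change from baseline is derived for BMD only, and that T-scores and Z-scores have absolute change only. Make the same restriction in the first sentence of section 12.3, and bring the table shells into line. Section 3.2.6 needs no edit, because it defines the endpoints as change from baseline.

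The cost is one sentence in each of two sections and fewer table rows. Data collection and design are unchanged, and no valid information is lost.

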6.4. VITAL SIGNS

Changes from baseline will be calculated for each vital sign parameter for each scheduled visit. Change from baseline for systolic and diastolic blood pressure will be calculated irrespective of whether the arm used for the blood pressure assessment is the same at both visits. The last on-treatment measurement will also be identified.

6.5. ECGs

Changes from baseline will be calculated for each ECG parameter for each scheduled visit. The last on-treatment measurement will also be identified.

